## R.16 Modified Rankin Scale (mRS) Instructions

### Instructions:

- The mRS is to be determined after the NIHSS has been determined and graded and by the same rater.
- The determination of the scale should be made from 5 to 0, i.e., the order presented.
- The purpose of the mRS is to record whether the patient is dead, severely, moderately, or slightly disabled and if not dead or disabled, whether the patient is performing all usual activities without symptoms or not. Because subjects and family members may understate the severity of disability, it is important for the rating clinician to understand that the mRS is a clinical scale and not a patient-reported outcome. The rater may ask questions but must assess the disability whether or not in agreement with the subject or family.

**5 Severe disability;** someone needs to be available at all times; care may be provided by either a trained or an untrained caregiver.

Question: Does the person require constant care?

**4 Moderately severe disability;** need for assistance with some basic ADL, but not requiring constant care.

Question: Is assistance essential for eating, using the toilet, daily hygiene, or walking?

**3 Moderate disability;** need for assistance with some instrumental ADL but not basic ADL.

Question: Is assistance essential for preparing a simple meal, doing household chores, looking after money, shopping, or traveling locally?

**2 Slight disability;** limitations in participation in usual social roles, but independent for ADL.

Questions:

- Has there been a change in the person's ability to work or look after others if these were roles before stroke?
- Has there been a change in the person's ability to participate in previous social and leisure activities?
- Has the person had problems with relationships or become isolated?
- Do any of the following interfere with the subject's ability to perform all usual activities: difficulty reading or writing, difficulty speaking or finding the right word, problems with balance or coordination, visual problems, numbness (face, arms, legs, hands, feet), loss of movement (face, arms, legs, hands, feet), difficulty with swallowing, or other symptom resulting from stroke?

**1 No significant disability;** symptoms present but not other limitations.

Question: Does the subject have any symptoms that do not interfere with the performance of all usual activities?

**0 No symptoms at all;** no limitations and no symptoms.

**Note:** The above questions are a modification of the questions from **Wilson, et. al, Stroke. 2002;33:2243-2246** and are **modified here for the use in percutaneous heart valve trials** for the FDA Division of CV Devices.

**R.17 Mini Mental State Exam (MMSE-2:SV)**

Mini Mental Status Exam1: The MMSE-2 Standard Version should be used.

**Procedure:**

Administer the MMSE-2 exam utilizing the standardized worksheets provided.

<http://www.minimental.com/>

## R.18 Additional Neurological Assessments

### Visual Field Testing

Visual fields, (upper and lower quadrants) are tested by confrontation, using finger counting or visual threat as appropriate.

Visual fields may be impaired by lesions anywhere in the neural visual pathways, from the optic nerves to the occipital lobes.

- **Individual eyes:**

In direct confrontation, examiner should sit directly in front of the patient, at the same level and approximately one meter apart. Ask the patient to cover one eye and maintain a fixed gaze on the examiners eye or nose. The examiner brings a small target (e.g. a match or a finger) from the periphery of the subject's visual field into each of the 4 visual quadrants and requests that the patient indicate when they first visualize the object. Wiggling the target assists in the patients separating and defining it.

Repeat the testing for the other eye.

Any abnormalities in target detection should prompt detailed testing with more precise instruments.

- **Bilateral eyes:**

In the same position, and with the patients fixed gaze on the examiners nose or eyes, use finger counting or visual threat to identify any asymmetry in the visual field.

### Gait Assessment

Not tested as part of the NIH Stroke Scale.

Ask the patient to walk down a straight hallway under observation, if ambulatory.

Note any apparent abnormalities of gait. (Ataxic, lateralized hemi-paretic, 'shuffling' or 'small-step' or other abnormality).

### Hand Function

- **Motor assessment**

The extensors are weaker than the flexors in the upper extremities. Consequently, following a neurological event, the arm eventually assumes a flexed position. Therefore the biceps will be stronger than the triceps, the wrist and finger flexors stronger than the extensors. For this reason it is not a good idea to monitor for stroke progression by testing grip strength. Test finger extensor strength instead.

Muscle power is classically graded on a scale of 0 – 5, with 0 being no power and 5 being normal power. For the purposes of documenting subtleties in potential deficits, power in finger muscle groups should be documented on a 0 – 10 scale as follows.

Grade 0	No muscle contraction
Grade 2	Muscle contraction without joint movement
Grade 4	Partial movement with gravity eliminated
Grade 6	Movement against gravity
Grade 8	Movement against some resistance
Grade 10	Normal strength

(Use odd numbers to document when physical findings fall between grades).

- **Finger Abductors**

Instruct the patient to “Spread your fingers apart, push your index finger towards the other hand. Don’t let me push it back”. Push on the finger at the Proximal Interphalangeal (PIP) joint level.

- **Finger Adductors**

Ask patient to ‘grip a sheet of paper’ between their fingers. Try to pull the sheet away from them.

- **Finger Extensors**

Instruct the patient to “Keep your fingers out straight, and don’t let me bend them”. This is a test of extension at the metacarpophalangeal (MCP) joints. It is important to support the palm and apply pressure to the PIP joints, testing extension at only one set of joints, because extension at the PIP joints is performed by the small hand muscles.

- **Sensory Assessment**

In a seated position, ask the patient to place both hands on their lap with palms facing down. Instruct them to close their eyes, and using their index finger point to the position touched by the examiner on fingers of the opposite hand. Repeat for both hands.

This should be documented as: ‘normal sensation’ or ‘can feel but unable to localize’ or ‘no sensation’ for each hand.

### **Writing Evaluation**

Ask the patient to write two sentences about a particular subject. (e.g. their hometown). There is no time limit, and patient can be given time prior to neurological examination as necessary.

Note the subject’s ‘use of paper’, including the position of writing. Also, note whether the written subject is appropriate to that asked, and the correctness of the grammar, spelling and syntax used.

Document as ‘fail’ or ‘pass’ or ‘subject unable to attempt test’ if patient is unable.

### **Drawing Assessment**

The ‘clock-drawing’ test is used for screening for cognitive impairment and dementia, and as a measure of spatial dysfunction and neglect. Doing the test requires verbal understanding, memory and spatially coded knowledge in addition to constructive skills.

Constructional apraxia may occur with lesions in either the left or right parietal lobe, although it is more frequent after right parietal damage (visually dominant).

Clock drawing has been used as a diagnostic measure of unilateral spatial neglect, with neglect patients omitting numbers on one half, with or without transposition of the numbers from the neglect side to the other, or demonstrating inattention to parts of the spatial layout of numbers.

The test has a high correlation with the MMSE and other tests of cognitive dysfunction.

- Ask patient to draw the face of a clock and put the numbers in the correct position.
- Then ask patient to draw in the hands at a particular time (e.g., “twenty minutes after eight”).
- There is no time limit.

One point will be assigned for each of the following items completed (draws closed circle, includes all 12 correct numbers, places numbers in correct positions, places hands in correct positions) for a total of four points.

## R.19 Medtronic CoreValve™ Clinical Assessment Guidelines

Clinical Assessments will be collected to help assess the overall health and frailty of study participants at the time of screening. These assessments include measures of nutrition, strength and balance, independence in average daily living, mental status, and medical comorbidities.

The following are guidelines provided for administering the strength and balance examination.

**5-Meter Gait Speed:** The Gait Test measures, in seconds, the time a person takes walk 5meters.

**Procedure:**

- Accompany the patient to the designated area, which should be well-lit, unobstructed, and contain clearly indicated markings at 0 and 5 meters
- Position the patient with his/her feet behind and just touching the 0-meter start line
- Instruct the patient to “**Walk at your comfortable pace**” until a few steps past the 5-meter mark (the patient should not start to slow down before the 5-meter mark)
- Begin each trial on the word “**Go**”
- Start the timer with the first footfall after the 0-meter line
- Stop the timer with the first footfall after the 5-meter line
- Repeat 3 times, allowing sufficient time for recuperation between trials

Note: Patient may use a walking aid (cane, walker). If the patient is receiving an IV drip, he/she should perform the test without the IV only if it can be interrupted temporarily without any potential risk to the patient, if not, then the patient may perform the test pushing the IV pole.

**Grip strength test:** The grip strength test is used to determine the strength in each of the participant's hands.

**Procedure:**

- Equipment: Hand Dynamometer
- Illustrate the use of the instrument to the participant prior to testing.
- The participant should be in a seated position.
- Ask the participant to squeeze the dynamometer with as much force as possible, being careful to squeeze only once for each measurement.
- Three trials should be made for the right hand followed by three trials for left hand with a pause of about 10-20 seconds between each trial to avoid the effects of muscle fatigue.
- The highest reading for each hand should be reported on the case report form.

 Fried LP et al. (2001). Frailty in older adults: Evidence for a phenotype. *Journal of Gerontology: Medical Science*, 56A (3), M146-M156.

## R.20 Katz Index of Independence in Activities of Daily Living

Activities Points (1 or 0)	Independence (1 POINT) NO supervision, direction or personal assistance	Dependence (0 Points) WITH supervision, direction, personal assistance or total assistance
BATHING  Points: _____	(1 POINT) Bathes self completely or needs help in bathing only a single part of the body such as the back, genital area or disabled extremity.	(0 POINTS) Needs help with bathing more than one part of the body, getting in or out of the tub or shower. Requires total bathing.
DRESSING  Points: _____	(1 POINT) Gets clothes from closets and drawers and puts on clothes and outer garments complete with fasteners. May have help tying shoes.	0 POINTS) Needs help with dressing self or needs to be completely dressed.
TOILETING  Points: _____	(1 POINT) Goes to toilet, gets on and off, arranges clothes, cleans genital area without help	(0 POINTS) Needs help transferring to the toilet, cleaning self or uses bedpan or commode.
TRANSFERRING  Points: _____	(1 POINT) Moves in and out of bed or chair unassisted. Mechanical transferring aides are acceptable.	(0 POINTS) Needs help in moving from bed to chair or requires a complete transfer.
CONTINENCE  Points: _____	(1 POINT) Exercises complete self-control over urination and defecation.	(0 POINTS) Is partially or totally incontinent of bowel or bladder.
FEEDING  Points: _____	(1 POINT) Gets food from plate into mouth without help. Preparation of food may be done by another person.	(0 POINTS) Needs partial or total help with feeding or requires parenteral feeding.

**TOTAL POINTS = \_\_\_\_\_**  
 6 = High (patient independent)  
 0 = Low (patient very dependent)

Slightly adapted from Katz S., Down, T.D., Cash, H.R. et al. (1970)  
 Progress in the Development of the Index of ADL. Gerontologist  
 10:20-30. Copyright The Gerontological Society of America

## **R.21 Investigator Brochure / Report of Prior Investigations for the Investigational Devices**

The geography-specific Investigator Brochure for the Medtronic CoreValve™ System and Medtronic CoreValve™ Evolut™ R System will be provided separately, as applicable.

## **R.22 Investigational Devices Instructions For Use**

The geography-specific Instructions For Use for the Medtronic CoreValve™ System and Medtronic CoreValve™ Evolut™ R System will be provided under separate cover.

## R.23 Radiation Exposure and Data Collection

The SURTAVI protocol requires several tests and procedures that expose subjects to radiation (angiograms, arteriograms and fluoroscopy). These tests and procedures are essential to appropriate patient selection and proper deployment of the study valves.

Procedure	Interval
Multi-slice Computed Tomography (MSCT) Angiogram	Screening
Coronary arteriogram	Screening Index Procedure – TAVI only
Aorotogram	Index Procedure – TAVI only

The following describes radiation exposure data collection requirements as well as parameters for additional subject follow-up.

### Follow-up and Data Collection

Data regarding subject radiation exposure will be collected at all protocol intervals where radiation test or procedures are required.

- Screening
- Index-Procedure (TAVI only)
  - Percutaneous Coronary Intervention (PCI) – if staged approach
- Reintervention (Valve related)

NOTE: Based on the protocol design, imaging required at screening may have been completed prior to the subject signing the informed consent form and data related to radiation exposure during the acquisition of the images may not be available. **Radiation exposure data missing from the subject record will not be considered a protocol deviation.**

### Substantial Radiation Dose Level

For purposes of SURTAVI, substantial radiation dose level (SRDL) is defined as meeting/exceeding one of the following:

Dose Metric	SRDL
Total air kerma at IRP ( $K_{a,r}$ )	3 Gy
Kerma-area product ( $P_{ka}$ )	250 Gy·cm 
Fluoroscopy Time	60 min

In cases where SRDL is met or exceeded additional steps should be taken.

- Document the radiation dose the subject was exposed to in the medical record
- Include an explanation regarding the medical necessity
- Describe the planned follow-up
- Notify the subject and caregiver, if applicable
  - Instruct subject (and caregiver) to perform visual skin assessments at least once per week between in-clinic visits
  - If a hand-sized red area or rash is noted, contact the Investigator immediately to schedule a follow-up visit

To ensure signs and symptoms of radiation exposure are identified as soon as possible, subjects should have a routine visual skin assessment at the following protocol intervals:

- Baseline
- Immediate Post-Procedure – within 48 hours of TAVI
- Discharge
- 30-days

Additional follow-up should be scheduled at the Investigators discretion based on progression of symptoms, as applicable.

If skin changes are noted at any interval additional follow-up should be scheduled with a dermatologist, or physician with the appropriate training and expertise for diagnosis and treatment. Long-term follow-up should be conducted in accordance with local standard of care.

Skin assessment findings should be noted in the patient medical record and applicable adverse events should be reported.

**Threshold for Radiation Dose Exposure**

**Chronology and Severity of Tissue Reactions From Single-Delivery Radiation Dose**

Single site (Gy) acute skin dose	Prompt (<2 weeks)	Early (2–8 weeks)	Mid term (6–52 weeks)	Long term (<40 weeks)
	No observable effects expected			
2-5	Transient erythema	Epilation	Recovery from hair loss	None expected
5-10	Transient erythema	Erythema, epilation	Recovery; high doses cause prolonged erythema and permanent partial epilation	Recovery; higher dose cause dermal atrophy/induration
10-15	Transient erythema	Erythema, epilation; dry/moist desquamation	Prolonged erythema permanent epilation	Telangiectasia; dermal atrophy/induration
>15	Transient erythema; Very high dose causes moist desquamation edema/ulceration	Erythema, epilation	Dermal atrophy with secondary ulceration; atrophy/induration; High dose dermal necrosis surgical repair likely	Telangiectasia; dermal Late skin breakdown

Modified: Balter S. Fluoroscopically guided interventional procedure: A review of radiation effects on skin and hair. NCRP SC 2–3, Feb 2010.

**List of Abbreviations**

Abbreviation	Term
Gy	Gray
IRP	Interventional reference point
KAP	Kerma area product
PSD	Peak skin dose
SDRL	Substantial radiation dose level

## R.24 SURTAVI Risk Model

Risk assessment is essential in the strategy to approach patients with valvular heart disease in general and AS in particular. Various risk models primarily focusing on short-term mortality have been validated for AS patients (30-38). Some were initially derived from a broader patient population undergoing any type of cardiac surgery, others were more explicitly tailored to patients with AS. Most notably, contemporary scoring models tend to be consistent in lower risk patients but diverge with increasing risk profile. This can be partly explained by the fact that these models were extracted from large databases where the average patient risk is fairly low. Therefore such models are less well validated for higher risk patients and expectedly perform less well in the “outlier” population currently considered for TAVI (39).

An in-depth reappraisal of existing scoring models reveals some concordant risk factors (e.g. age, gender) but also established risk factors that are clearly missing (e.g. mediastinal radiation, porcelain aorta and frailty) (40-42). Furthermore definitions of individual components are not uniform and do not correspond to current suggested guidelines/definitions by respective professional societies.

### R.24.1 SURTAVI Risk Model Rationale

#### 1. Joint database

Following the initial report by the Bern, Rotterdam collaboration (28) including 1122 patients with severe AS, four academic institutions in Bern, Rotterdam, Bad Nauheim and Munich have created a joint database on all consecutive patients with severe AS treated with either TAVI or SAVR between January 2006 and December 2009.

Preliminary analysis on 3688 patients has been performed, including 789 TAVI and 2899 SAVR patients.

The pre-specified primary outcome was all cause mortality at 1 year. Patients were actively followed up after the index procedure and their vital status confirmed by outpatient clinic visit, telephone contact, review of medical records or national civil registries.

[figure not shown]
#### 2. Statistical methods

The propensity scores of SAVR patients were estimated using a probit model with all baseline characteristics as described above as independent variables. The propensity score is the probability that a patient would have been treated with SAVR given that patient's observed baseline characteristics. To ensure the quality of the matching using propensity scores the common support assumption was applied, using the Epanechnikov kernel probability density estimates. The IPT weighted multivariable analysis was used. The IPT weighted analyses used the inverse of the propensity score as weights in SAVR patients and the inverse of 1 minus the propensity score in TAVI patients. All analyses were based on logistic regression models on the 1 year mortality and were performed in the overall dataset and stratified according to presence or absence of sufficient overlap of propensity scores (propensity score <0.675 versus ≥0.675).

[figure not shown]
#### 3. Type of patient (patient selection)

Preliminary analysis demonstrated a pre-dominance of patients with age >80 years old, and a logistic EuroSCORE <20% in the TAVI cohort (figure “scatterplot”). However, the majority of patients in the entire study population are between 65-and 83-years-old (figure “age distribution”).

**SURTAVI Clinical Investigation Plan - Appendix  
(Surgical Replacement and Transcatheter Aortic Valve Implantation)**

[figure not shown]

The distribution of age in patients treated for aortic stenosis. The color indicates the percentage of patients treated with TAVI in the corresponding age group

[figure not shown]

A scatterplot showing the age and corresponding EuroSCORE of patients treated for aortic stenosis. Indicated by colours are the treatment arms surgical aortic valve replacement and transcatheter aortic valve implantation. A previous commonly used EuroSCORE cut-off value of 20% is indicated in the graphic to show that many patients with lower scores are already treated by TAVI, but in lower ages this treatment remains limited due to the low EuroSCORE.

As it is well-known that both the STS score and EuroSCORE are suboptimal in operative risk assessment, these models are only used for descriptive purposes (39). Age is the predominant predictor of mortality in general, and after valve surgery in particular. Furthermore, the impact of other risk factors appears to be accentuated in an older age population.

Survival curves of the general Dutch population (derived from death register); and patients undergoing an AVR (derived from meta-analysis data), or an AVR with the additional risk factor of coronary sclerosis (derived from meta-analysis data).

The range of both the EuroSCORE and STS score in a patient with 2 risk factors. The lower boundary indicates a score with risk factors that have little influence on the score, while the upper boundary indicates a score with risk factors that influence the score significantly

Therefore, we opt for a risk assessment based on age in combination with encoded co-morbidities selected from a pre-specified listing. Patients at intermediate risk are defined as age 70-74 years with 2 or 3 co-morbidities (cohort 1); age 75-79 years with 1 or 2 co-morbidities (cohort 2); and patients ≥80 years of age with ≤1 co-morbidities (cohort 3).

In-depth analysis and translation of the risk profile mentioned above to the STS score (table STS below):

- Cohort 1: range of 0.9% to 10.2% in males, and 1.4% to 14.8% in females
- Cohort 2: range of 1.2% to 8.5% in males, and 1.8% to 12.4% in females
- Cohort 3\*: range of 1.7% to 8.9% in males, and 2.6% to 12.7% in females

Male		70 yr	73 yr	76 yr	79 yr	82 yr	85 yr	88 yr	91 yr
Risk factors	0	...	...	...	...	1.7	2.1	2.5	3.0
	1	...	...	1.2 - 3.6	1.4 - 4.3	1.7 - 5.2	2.1 - 6.2	2.5 - 7.4	3.0 - 8.9
	2	0.9 - 5.7	1.0 - 6.3	1.2 - 7.1	1.4 - 8.5	...	...	...	...
	3	1.1 - 9.3	1.2 - 10.2	...	...	...	...	...	...
Female		70 yr	73 yr	76 yr	79 yr	82 yr	85 yr	88 yr	91 yr
Risk factors	0	...	...	...	...	2.6	3.2	3.8	4.5
	1	...	...	1.8 - 5.4	2.2 - 6.5	2.6 - 7.7	3.2 - 9.2	3.8 - 10.9	4.5 - 12.7
	2	1.4 - 8.4	1.6 - 9.3	1.8 - 10.5	2.2 - 12.4	...	...	...	...
	3	1.7 - 13.5	1.9 - 14.8	...	...	...	...	...	...

STS score: ranges of scores are displayed as: score with least influential risk factors – score with most influential risk factors. \*Upper age limit 91 years old

In-depth analysis and translation of the risk profile mentioned above to the logistic EuroSCORE (Table EuroSCORE below):

- Cohort 1: range of 9.1% to 42.3% in males, and 12.2% to 50.5% in females
- Cohort 2: range of 7.2% to 32.1% in males, and 9.8% to 39.6% in females
- Cohort 3\*: range of 6.6% to 27.8% in males, and 9.0% to 34.9% in females

Male		70 yr	73 yr	76 yr	79 yr	82 yr	85 yr	88 yr	91 yr
Risk factors	0	...	...	...	...	6.6	8.0	9.6	11.4
	1	...	...	7.2 - 12.4	8.7 - 14.8	10.4 - 17.5	12.4 - 20.5	14.7 - 24.0	17.4 - 27.8
	2	9.1 - 20.6	10.9 - 24.0	13.0 - 27.9	15.4 - 32.1	...	...	...	...
	3	16.2 - 37.5	19.1 - 42.3	...	...	...	...	...	...
Female		70 yr	73 yr	76 yr	79 yr	82 yr	85 yr	88 yr	91 yr
Risk factors	0	...	...	...	...	9.0	10.7	12.8	15.2
	1	...	...	9.8 - 16.5	11.7 - 19.4	13.9 - 22.7	16.5 - 26.4	19.4 - 30.5	22.7 - 34.9
	2	12.2 - 26.5	14.5 - 30.6	17.2 - 35.0	20.2 - 39.6	...	...	...	...
	3	21.1 - 45.5	24.7 - 50.5	...	...	...	...	...	...

Euroscore: ranges of scores are displayed as: score with least influential risk factors – score with most influential risk factors. \*Upper age limit 91 years old

[figure not shown]

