## C.4 Trial Procedures

### C.4.1 Screening Procedures

Prior to any trial-specific tests or procedures, written informed consent must be obtained from the subject. Failure to obtain a signed and hand dated informed consent prior to the procedure constitutes a protocol violation, which is reportable to the IRB/MEC, the Food and Drug Administration (FDA), and other regulatory authorities as applicable.

All potential subjects for trial entry must be screened for eligibility. All patients with symptomatic severe AS that provide informed consent will be entered into the Electronic Data Capture (EDC) system and total number of patients screened will be counted. The reasons why a patient did not enter the Heart Team meeting will be collected (eg. patient does not meet inclusion criteria or meets an exclusion criteria) and, age, STS score, and available screening data.

Data readily available in the patient's medical record may be utilized to fulfill screening requirements and do not need to be repeated. If not previously completed, the following tests and procedures must be performed prior to randomization to verify eligibility. The recommended timeframe for these tests and procedures is within 30 days prior to submission to the Heart Team, unless otherwise specified.

- Demographics and Medical History
- Clinical Assessments – Refer to **Appendix R.19**
  - 5-Meter Gait Speed
  - Grip Strength
- Physical Examination including:
  - Vital signs, weight, height, and body surface area (BSA);
    - BSA will be calculated from height and weight by use of the formula by Dubois and Dubois ( $BSA = 0.007184 \times \text{weight [kg]}^{0.425} \times \text{height [m]}^{0.725}$ )
  - Major systems findings
- NYHA Classification
- Risk Assessments:
  - STS Risk Score – Dataset Version 2.73
  - Logistic EuroSCORE
  - EuroSCORE II
  - SYNTAX Score
  - Katz Index of Independence in Activities of Daily Living
- Co-morbidities
- Routine Laboratory Tests:
  - Complete Blood Count:
    - White Blood Count
    - Hematocrit
    - Hemoglobin
    - Platelet Count
  - Creatinine and Creatinine Clearance
  - Cardiac Enzymes (CK/CK-MB)
  - International Normalized Ratio (INR), if applicable
  - Activated Partial Thromboplastin Time (aPTT)
  - B-type Natriuretic Peptide (BNP) or NT-proBNP
  - Liver Panel:
    - ALT
    - AST
    - Albumin
  - Sodium
  - Potassium

- Transthoracic Echocardiogram (TTE)

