### C.6.5 Primary Analysis

The primary endpoint of all-cause mortality or disabling stroke at 24 months will be evaluated using the absolute difference of the TAVI rate and the SAVR rate for all-cause mortality or disabling stroke during a fixed follow-up of 24 months' time. The hypothesis test is designed to show non-inferiority of TAVI to SAVR for the primary endpoint.

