#### Sample Size Justification

The assumed values  $\pi_T = \pi_C = 0.17$  are based on the data published by Iturra et al and CoreValve US Pivotal High Risk study results. As reported in the Iturra paper, the incidence of all-cause mortality at 30 days was 2.8% and the late all-cause mortality Kaplan-Meier rate at 24 months was 12.1%. The overall 24-month all-cause mortality rate was approximately 15%. STS score reported in the Iturra paper ( $5.6 \pm 1.1$ , n=502) was similar to the STS score for subjects currently enrolled in the SURTAVI study ( $5.6 \pm 1.4$ , n=654), and it is believed that the 24-month all-cause mortality rate in SURTAVI will be approximately 15% at 24 months. The major stroke rate was 3.2% for subjects who survived to 1 year in the CoreValve Pivotal High Risk study. The High Risk study enrolled a higher-risk population than SURTAVI, therefore, the major stroke rate in the High Risk study is adjusted downward, and it is believed the disabling stroke rate at 24 months would be approximately 2% in the SURTAVI study. Overall, the estimation of the all-cause mortality or disabling stroke rate at 24 months is 17%.

Although the pre-specified analysis methods are Bayesian, the sample size is guided by a standard frequentist non-inferiority power analysis. Under the assumptions of  $\pi_T = \pi_C = 0.17$ , non-inferiority margin  $\delta=0.07$ , 1:1 randomization,  $\alpha= 0.05$ , and power = 95%, the method of Farrington and Manning as implemented in PASS 2008 indicates that the required sample size for a single-look analysis is 1258. To allow for up to 6% dropout, 1339 subjects must be accrued. Furthermore, to compensate for power lost in a two-look group sequential analysis plan using Pocock-type alpha spending, the sample size would have to be increased by about 12.5%. This leads to an estimated sample size of 1531. Thus a sample size of 1600 mITT subjects should provide ample power for establishing non-inferiority in the primary hypothesis test.

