The statistical approach for these analyses is Bayesian. The prior distributions for  $\pi_T$  and  $\pi_C$  in these calculations are Beta (1,1). The threshold  $\Psi$  is designated to be 0.971 for non-inferiority testing and  $\Psi_{\text{SUP}} = 0.989$  for superiority testing; these values are selected by trial-and-error to achieve a type I error (under simulation) of at most 0.05 for non-inferiority testing and at most 0.025 for superiority testing. Of note, establishing  $P(H_{\delta=0} | \text{data}) > \Psi_{\text{SUP}}$  means that superiority has been established to a standard equivalent to a nominal significance level of 0.025 (1-sided), but this does not automatically mean that a labeling claim of superiority is supported. See "Multiplicity Considerations" (Section C.12) for additional requirements regarding labeling claims on secondary objectives.

Further details of planned analyses are provided in the SAP.

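### The primary 24-month comparison, as the protocol states it, adjusts for neither age nor STS score: it is valid, but gives up a small amount of precision

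*Combined protocol and SAP*

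**What the plan says.** C.6.5 of the protocol states that the primary endpoint "will be evaluated using the absolute difference of the TAVI rate and the SAVR rate". C.6.5.1 defines these as binary rates over a fixed 24 months, with a margin of 0.07. The Analysis Plan under C.6.5.2 says that the priors for the two rates "in these calculations are Beta (1,1"), with posterior thresholds of 0.971 for non-inferiority and 0.989 for superiority. No baseline covariate enters, and C.6.6, whose heading covers planned sensitivity analyses, names no adjusted analysis.

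The screening list in C.4.1 includes demographics and "STS Risk Score – Dataset Version 2.73". C.4.5 and C.6.5.2 stratify randomisation by site and by need for revascularisation only.

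Appendix R.24.1, item 3, says that "Age is the predominant predictor of mortality in general, and after valve surgery in particular". The sentence before it calls the STS score and EuroSCORE suboptimal for operative risk and limits them to descriptive use.

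Age and STS score appear elsewhere only in ways that leave the primary estimate unchanged: baseline comparison by arm (C.6.3), poolability by baseline demographics (C.6.11), and exploratory subgroup interactions (C.6.12.1). C.6.5.2 refers the reader to the SAP for further detail.

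**The concern.** The composite is mostly mortality: the Sample Size Justification builds its 17% from about 15% deaths and 2% disabling strokes. If a variable recorded on everyone before randomisation predicts death, leaving it out keeps its share of the outcome variance in the posterior for the TAVI minus SAVR difference. A standardised analysis estimates the same marginal difference, so it can use the same margin and the same decision rules with a slightly narrower posterior. It also makes the estimate conditional on the age and risk mix actually enrolled in each arm.

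What is at stake is precision. This matters least for non-inferiority under equal rates, where the design has power to spare. It matters more for the superiority test, for which the protocol states no power, and for non-inferiority if TAVI is slightly worse.

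**Working it through.** **1. The plan's own figure.** Inputs from the Sample Size Justification: 17% in each arm, margin 0.07, alpha 0.05, power 95%, 1:1. The Farrington-Manning rates restricted to the null are 0.2105 and 0.1405. Per arm, n = [1.645 x sqrt(0.2105 x 0.7895 + 0.1405 x 0.8595) + 1.645 x sqrt(2 x 0.17 x 0.83)]^2 / 0.07^2 = 629, or 1258 in total. This matches the stated 1258 and shows that alpha is one-sided. Then 1258/0.94 = 1339, also as stated. The calculation is unadjusted throughout.

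**2. How much variance age or STS score might explain.** The documents give no R-squared. I take R-squared = Var(risk)/(0.17 x 0.83) = Var(risk)/0.1411.
- STS score: the Sample Size Justification gives 5.6 ± 1.4 for subjects enrolled so far. If 24-month risk is proportional to the score, R-squared = (0.17 x 1.4/5.6)^2/0.1411 = 1.28%.
- Age: in the R.24.1 STS table, with no risk factors, the score rises between ages 82 and 91 from 1.7 to 3.0 in men and from 2.6 to 4.5 in women. Per year this is (3.0/1.7)^(1/9) = 1.065 and (4.5/2.6)^(1/9) = 1.063, or about 6.4%. With an assumed age SD of 4, 5, 6 or 7 years, R-squared = (0.17 x 0.064 x SD)^2/0.1411 = 1.3%, 2.1%, 3.0% or 4.1%.
- Both together: a simulation of 1600 subjects with age SD 6 gave a variance 3.7% smaller for the standardised difference.
- Sensitivity: assumed odds ratios of 1.02 to 1.08 per year and 1.05 to 1.40 per STS point give R-squared of 0.3% to 5.9%.

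The working range is 1.3% to 4%.

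**3. Effect on power.** Adjustment multiplies the variance of the difference by about (1 - R-squared). Final look, 800 per arm, normal approximation: power = Phi(distance/SE - z), with SE^2 = (1 - R-squared) x [pT(1-pT) + pC(1-pC)]/800, and z = 1.896 for threshold 0.971 or 2.290 for 0.989. The distance is pC + 0.07 - pT for non-inferiority and pC - pT for superiority. The last two scenarios are illustrations, not protocol assumptions.

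| Scenario (TAVI v SAVR) | Unadjusted | R-squared 1.3% | R-squared 4% |
|---|---|---|---|
| Non-inferiority, 17% v 17% | 96.6% | 96.8% | 97.2% |
| Superiority, 12% v 17% | 71.1% | 71.8% | 73.1% |
| Non-inferiority, 19% v 17% | 76.1% | 76.6% | 77.7% |

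With the 6% missing data that the plan allows for (752 per arm), the rows run 95.7% to 95.9-96.4%, 68.1% to 68.7-70.1%, and 73.5% to 74.1-75.2%. The gains are about the same.

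**4. In subjects.** 1600 x 0.013 = 21 and 1600 x 0.04 = 64.

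**5. Chance imbalance.** At age SD 6, the SE of the between-arm age difference is 6 x sqrt(2/800) = 0.3 years. A 2-SE difference of 0.6 years shifts the event difference by 0.6 x 0.064 x 17 = 0.65 points. That is 9% of the 7-point margin, and about a third of the 1.88-point SE of the difference at 17% v 17%.

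**The case against.** **The comparison is already valid.** A reader might infer that chance imbalance in age or risk goes uncorrected and so biases the result. The documents do not support that. Randomisation makes the unadjusted comparison valid, and ordinary chance imbalance is already part of its posterior width and simulated type I error. This stands, and it limits the point to efficiency.

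**The gain is small and rests on extrapolation.** The STS slope concerns operative mortality, not 24-month death or disabling stroke, and the age SD is assumed. Inclusion criterion 1 restricts predicted operative risk to at least 3% and below 15%. The R.24.1 cohorts pair younger age with more co-morbidities, and their STS ranges barely move with age (men: 0.9-10.2%, 1.2-8.5%, 1.7-8.9%). Selection of this kind may flatten the age slope and lower R-squared. This also stands.

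**R.24.1 itself discounts the STS score.** That is true of the exploratory appendix. Elsewhere the protocol relies on the score: it informs eligibility, and the Sample Size Justification borrows an external death rate partly because STS scores match. Age alone would support the point.

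**The gain is not free.** The thresholds were tuned by simulation to the present model, and the change history records statistical updates agreed with FDA. The interim falls when 1400 subjects reach 12 months, so many 24-month outcomes will be incomplete and an adjusted model must handle them too. This stands as a cost.

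**An adjusted analysis may already exist.** A reader might infer that none is planned. Without the SAP, that cannot be concluded.

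**Conclusion.** The point holds as a small loss of efficiency in the primary analysis as the protocol states it. It is not an error and does not threaten the primary conclusion. At R-squared of 1.3% to 4%, adjustment is worth roughly 20 to 65 of 1600 subjects. It adds under 1 power point for non-inferiority at the plan's own 17% v 17%, and about 1 to 2 points for superiority at 12% v 17% or for non-inferiority with TAVI 2 points worse. The size rests on an assumed age SD and on an operative-mortality slope carried over to 24 months.

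A further reading to resist is that adjustment would repair the exclusion of randomised subjects with no attempted procedure from the mITT population. It would not restore them. C.6.4.2 provides an ITT analysis, which addresses that separate question.

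**What to change.** First check whether the SAP already contains an adjusted primary or supportive analysis. If not, before any unblinded look, pre-specify the following in C.6.5.2:
- a Bayesian logistic model for the 24-month endpoint with arm, continuous age and STS score, and stated weak priors;
- standardisation: average the predicted risks over all mITT subjects under TAVI and under SAVR, and take the posterior of the difference;
- the same 0.07 margin and the same two decision rules;
- the same handling at the interim of subjects without 24-month outcomes as the current model uses;
- Ψ and Ψ_SUP re-checked with the existing type I error simulation;
- the Beta(1,1) comparison kept as a sensitivity analysis.

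If the agreed primary model cannot be changed, name the standardised difference in C.6.6 as a pre-specified supportive analysis.

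The cost is protocol and SAP wording, one re-run of the calibration, and a slightly less simple primary model. No extra data, visits or subjects are needed.
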